9.1.4.2. Incomplete Dates

If the date of onset is incomplete, then the month and year (or year alone if month is not recorded) of onset determine treatment emergence as follows. The event is treatment emergent if the month and year of onset (or year of onset) of the event is the same as or after the month and year (or year) of date of first dose.

9.1.5. Summaries of Adverse Events

An overall summary of AEs will display, by treatment, the number and percentage of subjects who had any TEAE, whose strongest TEAE relationship to study drug is related or not related, whose maximum TEAE severity is mild, moderate, or severe, who had any SAE, any Serious TEAE, any TEAE leading to study discontinuation, and any TEAE leading to death.

The following summaries (number and percentage of subjects) of AEs (by SOC and PT) will be provided by treatment:

- All TEAEs
- All TEAEs by strongest relationship
- All TEAEs by maximum severity grade
- All Related TEAEs by maximum severity grade

CONFIDENTIAL Page 14 03DEC2021

- All Serious AEs
- All Serious TEAEs
- All TEAEs leading to study discontinuation
- All TEAEs leading to death

These summaries will present the number and percentage of subjects with at least one qualifying AE. Subjects may have more than one AE per SOC and PT. Each summary will be ordered by descending order of incidence of SOC and PT within each SOC.

In addition to the by-treatment summaries, data listings will be provided for the following:

- All AEs (with a flag indicating whether the event is treatment emergent)
- SAEs
- AEs leading to study discontinuation
- Deaths

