7.1.4 Assessing Severity (Intensity)

The Investigator will grade laboratory AEs and clinical AEs (based on discussions with study participants) using the NCI Common Terminology Criteria for Adverse Events v5.0:

- Mild (Grade 1)
- Moderate (Grade 2)
- Severe (Grade 3)
- Life-threatening consequences (Grade 4)
- Death related to AE (Grade 5)

Adverse events will be recorded on the eCRF at the severity reported by the investigator. If an ongoing AE worsens or increases in its severity or its relationship to the study drug changes, a new AE entry for the event should be entered on the eCRF.

The following is a link to the grading scale:

https://ctep.cancer.gov/protocolDevelopment/electronic_applications/docs/CTCAE_v5_Quick_R eference_5x7.pdf

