9.1.1. Severity

AEs are graded by the investigator as Grade 1 (mild), Grade 2 (moderate), Grade 3 (severe), Grade 4 (potentially life threatening) or Grade 5 (death) according to the NCI Common Terminology Criteria for Adverse Events version 5.0.

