	Normal	•	•		XX	XX	XX	XX	XX	XX	XX	XX	XX
		xx (xx.x) xx (xx.x) x	x (xx.x)	(xx.x)	(xx.x)	(xx.x)	(xx.x)	(xx.x)	(xx.x)	(xx.x)	(xx.x)	(xx.)
	High	•		•	xx	XX	XX	xx	xx	XX	XX	XX	· xx
	-	xx (xx.x) xx (xx.x) x	x (xx.x)	(xx.x)	(xx.x)	(xx.x)	(xx.x)	(xx.x)	(xx.x)	(xx.x)	(xx.x)	(xx.)

^[1] Worst (most extreme) values presented for CRP. Reference: Listing xx.x.x.x

date time

Table 14.3.1.1

Overall Summary of Treatment-Emergent Adverse Events
(Safety Population)

	GLS-1027	GLS-1027	Placebo	Overall
	120 mg	360 mg	(N=XX)	(N=XX)
	(N=XX)	(N=XX)		
ubjects with any TEAE	x (xx.x%)	x (xx.x%)	x (xx.x%)	x (xx.x%)
ubjects whose strongest TEAE relationship to study drug is	x (xx.x%)	x (xx.x%)	x (xx.x%)	x (xx.x%)
ubjects whose strongest TEAE relationship to study drug is out related [2]	x (xx.x%)	x (xx.x%)	x (xx.x%)	x (xx.x%)
ubjects whose maximum TEAE severity grade is grade 1 [3]	x (xx.x%)	x (xx.x%)	x (xx.x%)	x (xx.x%)
ubjects whose maximum TEAE severity grade is grade 2 [3]	x (xx.x%)	x (xx.x%)	x (xx.x%)	x (xx.x%)
ubjects whose maximum TEAE severity grade is grade 3 [3]	x (xx.x%)	x (xx.x%)	x (xx.x%)	x (xx.x%)
ubjects whose maximum TEAE severity grade is grade 4 [3]	x (xx.x%)	x (xx.x%)	x (xx.x%)	x (xx.x%)
ubjects with any SAE	x (xx.x%)	x (xx.x%)	x (xx.x%)	x (xx.x%)
ubjects with any Serious TEAE	x (xx.x%)	x (xx.x%)	x (xx.x%)	x (xx.x%)
ubjects with any TEAE leading to study discontinuation	x (xx.x%)	x (xx.x%)	x (xx.x%)	x (xx.x%)
ubjects with any TEAE leading to death	x (xx.x%)	x (xx.x%)	x (xx.x%)	x (xx.x%)

AE = Adverse Event; SAE = Serious Adverse Event; TEAE = Treatment-Emergent Adverse Event;

^[1] Related TEAEs are those with a relationship of related, possibly related, or probably related. If the relationship is missing, it is considered related.

^[2] Not related TEAEs are those with a relationship of unlikely related or not related.

^[3] Severity grades are determined according to the NCI Common Terminology Criteria for Adverse Events version 5.0. Reference: Listing 16.2.7.1

Table 14.3.1.2

Treatment-Emergent Adverse Events by System Organ Class and Preferred Term (Safety Population)

System Organ Class	GLS-1027	GLS-1027	Placebo	Overall
Preferred Term	120 mg	360 mg	(N=XX)	(N=XX)
	(N=XX)	(N=XX)		
Subjects with at least				
one TEAE	x (xx.x%)	x (xx.x%)	x (xx.x%)	x (xx.x%)
<system #1="" class="" organ=""></system>	x (xx.x%)	x (xx.x%)	x (xx.x%)	x (xx.x%)
<preferred #1="" term=""></preferred>	x (xx.x%)	x (xx.x%)	x (xx.x%)	x (xx.x%)

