AEs are coded using MedDRA version 23.0 and ordered by descending order of overall incidence of SOC and overall incidence of PT within each SOC. At each level of summation (overall, SOC, PT), subjects reporting more than one TEAE are counted only once using the strongest relationship. Related TEAEs are those with a relationship of related, possibly related, or probably related. If the relationship is missing, it is considered related. Not Related TEAEs are those with a relationship of unlikely related or not related. Reference: Listing 16.2.7.1

Page 1 of x

GeneOne Life Science Inc. Protocol: GLS27-005

Table 14.3.1.4

Treatment-Emergent Adverse Events by System Organ Class, Preferred Term, and Maximum Severity Grade
(Safety Population)

System Organ Class				
Preferred Term	Grade 1	Grade 2	Grade 3	Grade 4
Subjects with at least one TEAE	x (xx.x%)	x (xx.x%)	x (xx.x%)	x (xx.x%)
<system #1="" class="" organ=""></system>	x (xx.x%)	x (xx.x%)	x (xx.x%)	x (xx.x%)
<preferred #1="" term=""></preferred>	x (xx.x%)	x (xx.x%)	x (xx.x%)	x (xx.x%)
<preferred #2="" term=""></preferred>	x (xx.x%)	x (xx.x%)	x (xx.x%)	x (xx.x%)
<system #2="" class="" organ=""></system>	x (xx.x%)	x (xx.x%)	x (xx.x%)	x (xx.x%)
<preferred #1="" term=""></preferred>	x (xx.x%)	x (xx.x%)	x (xx.x%)	x (xx.x%)
<preferred #2="" term=""></preferred>	x (xx.x%)	x (xx.x%)	x (xx.x%)	x (xx.x%)

AE=Adverse Event; TEAE = Treatment-Emergent Adverse Event; MedDRA = Medical Dictionary for Regulatory Activities

AEs are coded using MedDRA version 23.0 and ordered by descending order of overall incidence of SOC and overall incidence of PT within each SOC.

At each level of summation (overall, SOC, PT), subjects reporting more than one TEAE are counted only once using the highest grade.

Severity grades are determined according to the NCI Common Terminology Criteria for Adverse Events version 5.0.

Reference: Listing 16.2.7.1

Repeat Table Layout for:

Table 14.3.1.5

Related Treatment-Emergent Adverse Events by System Organ Class, Preferred Term, and Maximum Severity Grade (Safety Population)

Table 14.3.2.1 Serious Adverse Events by System Organ Class and Preferred Term (Safety Population)

System Organ Class Preferred Term	GLS-1027 120 mg (N=XX)	GLS-1027 360 mg (N=XX)	Placebo (N=XX)	Overall (N=XX)
Subjects with at least one serious AE	x (xx.x%)	x (xx.x%)	x (xx.x%)	x (xx.x%)
<system #1="" class="" organ=""></system>	x (xx.x%)	x (xx.x%)	x (xx.x%)	x (xx.x%)

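### The maximum-severity displays stop short of Grade 5, so a subject with a fatal TEAE has no severity cell

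*SAP*

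**What the plan says.** The grading scale has five levels in both documents. SAP 9.1.1 ends its list with "Grade 4 (potentially life threatening) or Grade 5 (death) according to the NCI Common Terminology Criteria for Adverse Events version 5.0". Protocol 7.1.4 also makes the fifth level a recordable grade, worded as "Death related to AE (Grade 5" (closing bracket omitted here).

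The planned displays use shorter scales:

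- **SAP 9.1.5, overall summary:** subjects "whose maximum TEAE severity is mild, moderate, or severe". That is three categories.
- **SAP Appendix C, Table 14.3.1.1:** four maximum-severity rows. The last is for subjects "whose maximum TEAE severity grade is grade 4".
- **SAP Appendix C, Table 14.3.1.4**, titled "Treatment-Emergent Adverse Events by System Organ Class, Preferred Term, and Maximum Severity Grade": columns for Grades 1 to 4. Table 14.3.1.5, for related TEAEs, repeats this layout.

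The footnote to Table 14.3.1.4 gives the counting rule: "subjects reporting more than one TEAE are counted only once using the highest grade".

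**The concern.** A table of maximum severity should place every subject who had a TEAE in exactly one category. Here the top category of the defined scale is absent from the shells, and the 9.1.5 text leaves out the top two. The subjects left without a place are those with the worst possible outcome.

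What is at stake is the severity distribution by arm, and in particular Table 14.3.1.5. That table combines relationship to study drug with maximum grade, and as laid out it cannot show a fatal event judged related. Protocol 8.5.1 calls for adverse event frequencies by maximum severity, and a display without the highest grade does not fully deliver that.

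**Working it through.** There is no stated figure to reproduce, so the check compares the scales and then asks whether the gap is likely to matter in practice.

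**1. Scales side by side**

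| Place | Categories | Highest category |
|---|---|---|
| SAP 9.1.1; Protocol 7.1.4 | 5 | Grade 5, death |
| SAP 9.1.5, overall summary | 3 | severe (Grade 3 in SAP 9.1.1) |
| Table 14.3.1.1 shell | 4 | Grade 4 |
| Table 14.3.1.4 shell, repeated for 14.3.1.5 | 4 | Grade 4 |

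The text and the shells fall short of the defined scale, and they also disagree with each other.

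**2. Effect of the counting rule.** Let n1 to n5 be the numbers of subjects in an arm whose maximum TEAE grade is 1 to 5. If every TEAE is graded, subjects with any TEAE = n1 + n2 + n3 + n4 + n5. The shells print n1 to n4, so the printed grades fall short of the any-TEAE count by n5. The 9.1.5 text, taken literally, falls short by n4 + n5. A programmer who meets a Grade 5 maximum must either leave the subject out or enter the subject at a lower grade, which contradicts the footnote. The SAP does not say which.

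**3. Whether another SAP rule fills the gap.** Appendix A says that categories with zero counts are still shown, so Grade 5 would belong in the table even if nobody died. Appendices A and B allow tables to be combined, split or reorganised during programming. Neither says that a missing grade will be added.

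**4. Whether a related death can be seen in another summary table.** Table 14.3.2.4 shows TEAEs leading to death but not relationship. Table 14.3.1.3 shows relationship but neither grade nor fatal outcome. The combination is visible only by subject, in Listings 16.2.7.1 and 16.2.7.2, which give severity, relationship and outcome together.

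**5. Whether the cell is likely to be needed.** The documents give no overall mortality for the enrolled population, so a rate p has to be assumed. With 132 subjects:

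P(at least one death) = 1 − (1 − p)^132

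| Assumed p | Expected deaths, 132 × p | P(at least one death) |
|---|---|---|
| 1% | 1.32 | 0.73 |
| 2% | 2.64 | 0.93 |
| 5% | 6.6 | 0.999 |

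An empty Grade 5 cell cannot be relied on even at low mortality.

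**The case against.** The strongest reply is that fatal events are not lost. Table 14.3.1.1 has its own row for TEAEs leading to death. Table 14.3.2.4 gives fatal TEAEs by system organ class, preferred term and arm. They also enter the SAE tables, Listings 16.2.7.1 and 16.2.7.2 and the deaths listing (16.2.7.4), and Table 14.2.1.1 counts deaths as maximum WHO level 8. A Grade 5 row would largely repeat the death row. This stands, and it limits the seriousness of the point. A reader who inferred that deaths are hidden, or that the primary safety objective is compromised, would go too far: that objective is SAE incidence, and its displays are intact.

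A second reply is that the shells are mock-ups. The list of tables in 9.1.5 promises summaries by maximum severity grade without any upper limit, and nothing instructs anyone to drop Grade 5 subjects. The Table 14.3.1.4 shell, as available for review, also shows no treatment headings, so it may be incomplete. The row labels in Table 14.3.1.1 are therefore the firmer evidence. This has some weight, but those rows and the 9.1.5 wording are clear, and neither reaches Grade 5.

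Two stronger inferences are tempting and are not supported:

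- **That the arm with more deaths will show fewer subjects at the top of the scale.** Grade 4 counts depend on non-fatal life-threatening events, and a sicker arm could have more of both. Distortion is possible but not certain.
- **That 11 to 18 of 44 placebo subjects would go missing.** This multiplies background rates in Protocol 1.1: 44 × 0.50 × 0.50 = 11 and 44 × 0.50 × 0.80 = 17.6. That 50% describes progression to ventilation among patients who need supplemental oxygen, while the trial also enrols WHO level 3, without oxygen. The 50% in SAP section 4 is composite treatment failure, not ventilation. The product also assumes that every death is recorded as a Grade 5 TEAE. It is an upper scenario, not an expected count.

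**Conclusion.** The point holds as a minor display error that is wrong as written. If the 9.1.5 text and the three shells are followed, a subject whose maximum grade is 5 has no severity cell, the grades do not sum to subjects with any TEAE, and a related death has no place in Table 14.3.1.5. The between-arm severity comparison could be distorted if deaths differ by arm.

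The size in subjects cannot be derived from the documents. The probabilities of 0.93 and 0.999 rest on assumed mortality of 2% and 5%, equal and independent across subjects; to apply to the missing cell, they also need the death to be recorded as a Grade 5 TEAE. They show that the cell is likely to be needed, not how many subjects it would hold. Sample size, the primary efficacy analysis and SAE incidence are not affected.

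**What to change.** In SAP 9.1.5, replace the three severity words with maximum severity Grade 1 to 5. Add a Grade 5 row to Table 14.3.1.1 and a Grade 5 column to Tables 14.3.1.4 and 14.3.1.5.

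The cost is one sentence and three shell edits. No new data are needed, because SAP 9.1.1 and Protocol 7.1.4 already have investigators grade on the five-level scale.

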	9.1	С	Confidentiality	41
	9.2	S	Source Documents	41
	9.3	D	Data Collection	41
	9.4	R	Record Retention	41
	9.5	S	Safety and Quality Monitoring and Record Availability	41
	9.6	Α	Adverse event (AE) Reporting	42
	9.	6.1	Study Reporting Period of Adverse Events	42
	9.	6.2	Study Reporting Period for Serious Adverse Events	42
	9.	6.3	Notification of Serious Adverse Events	43
	9.7	S	Study Termination	43
1().	PU	BLICATION OF RESEARCH FINDINGS	44
1'	1.	LIS	ST OF ABBREVIATIONS	44
12	2.	RE	FERENCES	45
1:	3.	APF	PENDICES	47

List of Figures

FIGURE 1.1.1.1-1: PULMONARY LPS-INDUCED INFLAMMATION IS INHIBITED BY GLS-1027	15
FIGURE 1.1.1.1-2: PULMONARY LPS-INDUCED INFLAMMATION IS INHIBITED BY GLS-1027	16
FIGURE 1.1.1.2-2: GLS-1027 LOWERS PM2.5 INDUCED LUNG INFLAMMATION AND AIRWAY	
RESISTANCE	18
FIGURE 1.1.1.3-1: SARS-COV CASE-FATALITY RELATIVE TO PROVINCIAL AIR POLLUTION	
INDEX	19
FIGURE 1.2-1: STRUCTURE OF GLS-1027	21
FIGURE 1.2-2: STRUCTURE OF MICROCRYSTALLINE CELLULOSE	22

List of Tables	
TABLE 5.2-1. GLS-1027 AND PLACEBO DRUG PRODUCT VIAL LABELS	27

CLINICAL PROTOCOL SYNOPSIS

Title of study: Safety, Tolerability, Efficacy and Dose Response of GLS-1027 in the Prevention of Severe Pneumonitis caused by SARS-CoV-2 Infection

Number of study participants: 132

Study Phase: II

Study Type: Randomized, double-blind, placebo-controlled

Research Hypothesis: GLS-1027 will be safe, well tolerated and reduce the incidence of treatment failure as characterized by 1) advancing to WHO COVID-19 Classification level ≥6 which includes the need for intubation with mechanical ventilation, initiation of extracorporeal mechanical oxygenation (ECMO), or death, in SARS-CoV-2 infected hospitalized patients, 2) need for institution of salvage therapy 72 hours after study entry with either an IL-6 monoclonal antibody or dexamethasone (≥6 mg/day), 3) withdrawing consent from the study, 4) becoming lost to follow-up, or 5) discontinuation of treatment for any reason other than decrease in renal function or pregnancy.

Primary study objectives and outcome variables:

- Incidence of serious adverse events relative to treatment group
- Incidence of treatment failure within 28 days from enrollment

Exploratory study objectives and outcome variables:

- Assess the number of days requiring ICU care relative to treatment group
- Assess the number of days of mechanical ventilation relative to treatment group

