4.4 Discontinuation/Withdrawal of Study Participants

The Informed Consent will require that subjects allow follow-up for the primary outcome and safety through to 56 days post-enrollment or death. A subject may withdraw from the study by withdrawing consent to continue participation. If a subject withdraws consent from participating in the study at any time after enrollment, but prior to the final scheduled study visit, the investigator will make every effort to have the participant complete all assessments at the time of withdrawal. All data collected up to the time of withdrawal will be used for data analyses. The request to withdraw consent must be documented.

Discontinuing treatment is not a reason for withdrawing from participating in the study. Subjects who discontinue treatment for any reason should be followed until 56 days postenrollment or death, whichever comes first.

Reasons for treatment discontinuation are defined below.

- The PI or Medical Monitor consider that continuation of treatment may pose a safety risk to the subject. Treatment discontinuation will be considered a treatment failure, unless the subject discontinues treatment due to pregnancy or renal insufficiency. The subject should however continue to be monitored as per protocol for outcome measures through to study end (Day 56).
- Adverse event (Adverse Reaction): clinical or laboratory events that in the medical judgement of the investigator are grounds for discontinuation of treatment. This will be considered as a treatment failure. Subjects should however continue to be monitored as per protocol for outcome measures through to study end (Day 56).
- Lost to follow-up: for subjects who are discharged from the hospital within 28 days of treatment initiation who cannot be contacted after multiple attempts, will be

considered as Lost to Follow-up for purposes of Long-term outcomes (56 days). Otherwise, without relapse of COVID-19 symptoms, discharge within 28 days of enrollment is considered a treatment success. For subjects who are discharged from the hospital, every effort should be made to contact the subject to determine clinical status and adverse events post-discharge.

• Transfer of subject to another hospital. All transfers will be considered treatment failures.

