Any permanent stoppage of study drug in response to meeting any of the individual stopping rules will be considered as meeting study endpoint for failure except for a diagnosis of pregnancy, or stoppage related to decreased renal function.

Pause in Treatment or Termination of clinical trial

The Medical Monitor or DSMB may recommend global pause of study drug administration to all enrolled subjects if a safety signal is encountered that requires investigation and in the opinion of either the Medical Monitor or DSMB that continuation during the investigation period would present a safety risk to enrolled subjects. The decision to reinstitute study medication may be made at the conclusion of the investigation. The IRB will be informed of all such treatment interruptions and will be provided a report of the investigation.

Except for detection of a safety signal, the study will continue to the target enrollment unless enrollment has been increased to gain additional statistical power for assessing dose dependent response.

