3. STUDY DESIGN AND PLAN

This is a Phase II, randomized, double-blind, placebo-controlled study to assess 2 dose levels of GLS-1027 for the prevention of treatment failure among participants admitted to the hospital with PCR confirmed infection with SARS-CoV-2 (WHO classification 3 or 4). Subjects can be enrolled up to 72 hours from the time of hospital admission.

Participants will be randomized to placebo or GLS-1027 at either 120 mg or 360 mg daily in a 1:1:1 ratio as adjunctive to standard of care based on the hospital COVID-19 treatment algorithm and/or local COVID-19 treatment practices. Participants will be administered study drug for a maximum treatment period of 14 days or until discharge or death, whichever comes first. Primary outcome will be assessment at day 28, with follow-up to continue to Day 56 to document AEs and outcome as to discharge, death, or WHO COVID-19 classification level if subject remains hospitalized.

All subjects will be considered to have completed the study except for the following circumstances:

- Withdrawal of consent from study
- Loss to follow-up
- Stopped study treatment for any reason other than discharge, pregnancy, or decreased renal function

Table 1: Schedule of Assessments

Tests and Observations	1	2	3	4	5	6	7	8	9	10	11	12	13	14	15	28	56 ^m
Clinical Evaluations																	
Obtain written Informed Consent	Х																
Confirm Eligibility Criteria	Х																
Demographics	Х																
Medical History	Х																
Concomitant Medications	Х	Х	Х	Х	Х	Х	Х	Х	Х	Х	Х	Х	Х	Х	Х	Х	Х
Review Medical Record	Х	Х	Х	Х	Х	Х	Х	Х	Х	Х	Х	Х	Х	Х	Х	Х	Х
WHO COVID-19 Classification (Appendix B)	Х	Х	Х	Х	Х	Х	Х	Х	Х	Х	Х	Х	Х	Х	Х	Х	Х
Safety Evaluations																	
Record Adverse Events	Х	Х	Х	Х	Х	Х	Х	Х	Х	Х	Х	Х	Х	Х	Х	Х	Х
Record AM Vital Signs a	Х	Х	X	Х	Х	Х	Х	Х	Х	Х	Х	Х	Х	Х	Х		
Record Hematology ^b	Х	Х	Х			Х			Х			Х			Х		
Record Basic Metabolic Panel ^c	Х	Х	Х	Х	Х	Х	Х	Х	Х	Х	Х	Х	Х	Х	Х		
Record liver function studies (LFTs) °	Х					Х			Х			Х			Х		
Record other labs ^d (for days available)	Х	Х	Х	Х	Х	Х	Х	Х	Х	Х	Х	Х	Х	Х	Х		
Record Procalcitonin (baseline value) e	Х																
Record admission CXR	Х																
Record if care given in ICU setting	Х	Х	Х	Х	Х	Х	Х	Х	Х	Х	Х	Х	Х	Х	Х		
Record whether nasal O ₂ prescribed and dose level (L/min) ^f	Х	Х	Х	Х	Х	Х	Х	Х	Х	Х	Х	Х	Х	Х	Х		
Record whether CPAP prescribed and expiratory pressure ⁹	X	X	X	X	Х	Х	X	Х	Х	X	Х	Х	X	Х	X		

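### The SAP's adverse-event discontinuation outputs select on study discontinuation, which SAP 3 and Protocol 4.4 treat differently, and no table shows which adverse events stopped or interrupted study drug

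*SAP*

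**What the plan says.** SAP 9.1.5 lists, among the summaries by system organ class and preferred term, "All TEAEs leading to study discontinuation", and among the listings "AEs leading to study discontinuation". These become a row of Table 14.3.1.1, Table 14.3.2.3 and Listing 16.2.7.3. No output by event term is keyed to stopping or interrupting study drug.

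Protocol 4.4 separates the two events: "Discontinuing treatment is not a reason for withdrawing from participating in the study", and "Subjects who discontinue treatment for any reason should be followed until 56 days postenrollment or death, whichever comes first". One of its listed reasons for stopping treatment is "clinical or laboratory events that in the medical judgement of the investigator are grounds for discontinuation of treatment".

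SAP 3 draws the line elsewhere. Among the circumstances in which a patient has not completed the study it includes "Stopped study treatment for any reason other than discharge, pregnancy, or decreased renal function".

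Protocol 7.3.2 names two causes for discontinuing drug (items 1 and 2) and thirteen for halting it temporarily (items 3 to 15), with restart after resolution or improvement in most cases. It treats "Any permanent stoppage of study drug in response to meeting any of the individual stopping rules" as treatment failure, apart from pregnancy and renal stops.

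**The concern.** Tolerability is in the trial's title, and the synopsis hypothesis is that "GLS-1027 will be safe, well tolerated and reduce the incidence of treatment failure". Adverse events that make clinicians stop or hold a drug are direct evidence on that question, and the trial compares two doses with placebo. A reader of the study report would look for that evidence in Table 14.3.2.3. If the table selects on leaving the study, in a trial that asks patients who stop drug to stay, it may omit the patients of interest. Two programmers working from the same SAP could also produce different counts. Renal stops deserve particular attention, because Protocol 1.1.2 reports that 90% of the drug is excreted unchanged in urine.

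**Working it through.** The point is one of definition, so the check sets the texts side by side. The documents state no figure to reproduce.

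**Step 1: what the SAP's selection term can mean.** The SAP does not say how study discontinuation is derived for the adverse event tables. There are two candidates.

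- *Protocol 4.4 reading:* the patient leaves the study. Listing 16.2.7.1 shows a Yes/No Study Discontinuation column separate from Action Taken, which is compatible with this.
- *SAP 3 reading:* the patient is a non-completer, which includes stopping drug for most reasons. SAP 7.1 and Table 14.1.1.1 then report non-completers by reason.

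The table shell does not settle it. The source line of Table 14.3.2.3 points to Listing 16.2.7.4, which is the listing of deaths.

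**Step 2: who is counted under each reading.**

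| Situation | Protocol 4.4 reading | SAP 3 reading |
|---|---|---|
| Permanent stop for a non-renal adverse event, patient followed to Day 56 | missed | can be counted |
| Stop for decreased renal function, patient followed | missed | missed |
| Temporary hold for an adverse event, drug resumed | missed | missed |
| Adverse event after which the patient leaves the study | counted | counted |

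**Step 3: which holds matter.** Items 3 to 15 make 15 − 3 + 1 = 13 criteria. Item 4 (intubation or ECMO) is disease progression and appears in Table 14.2.1.1 through WHO levels 6 and above. Item 5 is inability to take drug orally. Item 3 is renal function. Items 6 to 15, which number 15 − 6 + 1 = 10, are laboratory or clinical events such as bilirubin or transaminase elevation, neutropenia, arrhythmia and gastric hemorrhage. Item 15 (opportunistic infection) is listed as a temporary halt but is excepted from restart, so it behaves as a permanent stop.

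**Step 4: whether another output fills the gap.**

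- Table 14.2.1.1 has a row by arm for stopping drug before discharge. It is all-cause and gives no event term. SAP 8.1 exempts renal suspensions and the other temporary cessations from failure.
- Table 14.1.5 gives exposure and doses missed by arm, without cause.
- Listing 16.2.5.2 gives the reason a dose was not given, and Listing 16.2.7.1 gives Action Taken. Both are patient-level and neither is summarised by arm.
- The tables of treatment-emergent events by relationship and grade, and those of serious events and deaths, do not show the consequence for dosing.

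**Step 5: scale, by assumption only.** Suppose 5% to 15% of an arm of 44 stopped drug permanently for a non-renal adverse event and all stayed in follow-up. That is 0.05 × 44 = 2.2 to 0.15 × 44 = 6.6, or about 2 to 7 patients. Table 14.3.2.3 would show none of them on the Protocol 4.4 reading and could show all of them on the SAP 3 reading. The rates are illustrative; the documents give none.

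**The case against.** A reader might infer that the trial has no valid table of tolerability. The documents do not support that. SAP 9.1.5 plans tables of all treatment-emergent events, by relationship and by maximum grade, with serious events and deaths. SAP 9.2 and 9.4 add laboratory shifts and QTcF categories. The primary safety objective is the incidence of serious adverse events, which this point does not touch.

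A reader might also infer that the discontinuation table must come out near zero in every arm. That follows on one reading only. On SAP 3's definition, permanent stops for non-renal events can enter the table, and disposition would report them by reason and arm. How sites would complete the Study Discontinuation field is unknown, since the CRF is not among the documents. An excess of stops or holds in one arm would also show in doses missed.

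Finally, the SAP cites protocol version 5.0 and a 14-day treatment period, while the supplied protocol describes 28 days. It may be a different version, and section 4.4 may read differently in version 5.0.

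All of this stands and limits the point. It does not remove it: the derivation is unstated, and the gap for renal stops and temporary holds exists even on the SAP's own definition.

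**Conclusion.** The concern holds as an ambiguity plus a gap. Who enters the adverse-event discontinuation outputs depends on which definition the programmer adopts. Under neither definition does any planned table show, by arm and event term, the renal stops or the adverse-event-driven holds. The number of patients affected cannot be estimated from the documents.

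The effect is confined to descriptive safety reporting. It is still worth correcting before unblinding, because tolerability is a stated aim and the correction is small. The contradiction with Protocol 4.4 assumes that version 5.0 keeps the supplied wording; the omission of renal stops and holds follows from the SAP's own definition and table shells.

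**What to change.** 1. In SAP 9.1.5, Tables 14.3.1.1 and 14.3.2.3 and Listing 16.2.7.3, change the selection to treatment-emergent adverse events leading to permanent discontinuation of study drug, derived from Action Taken and including renal adverse events. Correct the source line of Table 14.3.2.3.
2. Add a matching row in Table 14.3.1.1 and one table by system organ class and preferred term for events leading to interruption of study drug.
3. Report pregnancy stops in disposition. Protocol 7.1.1 excludes uncomplicated pregnancy from adverse events, so such stops do not belong in these tables.
4. Reconcile the completion definition in SAP 3 with Protocol 4.4, so that stopping drug and leaving the study are defined and reported separately.

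The cost is SAP wording and one extra table. Protocol 7.2 already requires the action taken for each adverse event, so no new data are needed if the codes distinguish drug withdrawn from drug interrupted. That should be confirmed against the CRF. No clinical rule changes.
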